11.3. Assessment of Suicidality at Screening

In the Screening for study eligibility for Phase 1 (AIAN women only) and Phase 3, the study staff will use three items from the Concise Health Risk Tracking-Self Report (CHRT-SR) Suicidal Behavior Evaluation (CHRT-SR) (Trivedi et al., 2011), a self-report assessment of suicidality and related thoughts and behaviors. The scale assesses suicidality quickly and easily in a manner consistent with the Columbia Classification Algorithm of Suicide Assessment (C-CASA) (Posner et al, 2007). The CHRT-SR will assess high risk for suicidality by a positive response ("Agree" or "Strongly Agree") on the last three questions (thoughts of, thoughts of how, and/or a specific plan to commit suicide) and prompt a clinician assessment for suicide risk before ending the screening visit. A study clinician will complete the Concise Health Risk Tracking – Clinician Rated (CHRT-CR) (Trivedi et al, 2011) to aid in his or her assessment of symptoms and he/she will initiate referral for additional mental health assessment and care as described in the DSMP.

12. PREMATURE WITHDRAWAL OF PARTICIPANTS

Participants in either Phases 1 or 3 may withdraw voluntarily from the study at any time. If they would like to withdraw from the study, they should contact the LI. They will be advised whether they need to complete any additional tests for their safety.

All participants will be followed for the duration of the study CTN-0123 unless they withdraw consent, die, or the investigator or sponsor decides to discontinue their enrollment for any reason. Reasons for the investigator or sponsor terminating a participant from the study may include, but are not limited to

- The participant becoming a threat to self or others
- The participant not following instructions
- The participant relapses on opioids while pregnant
- Staying in the study would be harmful for the participant
- Lack of funding
- The study is canceled

The participant may choose to stay in the study if they never use or discontinue their use of the Facebook intervention.

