8.4 Participant Exclusion Criteria

AIAN potential participants in Phases 1 and 3 meeting any of the exclusion criteria listed below will be excluded from study participation. Interested party participants in Phase 1 will only fail the screening if they meet the second exclusion criterion.

- (1) Self-reports current suicidality
- (2) Inability or unwillingness of participant to provide verbal consent (Phase 1) or written informed consent (Phase 3)
- (3) (Phase 3 only) Was a participant in Phase 1

Pregnant women, lactating women, or women who plan to become pregnant will not be excluded because the treatment being evaluated is a behavioral intervention and does not involve medication or risk to the fetus.

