10.3.7. Discontinuation of Study Intervention

If the subject never engages in the Facebook group or discontinues from the intervention but not from the study, remaining study procedures will be completed as indicated by the study protocol.

If a clinically significant finding is identified (including, but not limited to changes on the K6 scale from baseline) after enrollment, the investigator or qualified designee will determine if any change in participant management is needed. Any new clinically relevant finding will be reported as an adverse event (AE) if it meets the definition specified in Appendix A of the protocol. A plan is in place for clinical management of depression and other psychiatric symptoms or medical problems. The study staff will refer participants to the appropriate on-call physician or behavioral health clinician at the appropriate medical facility. The study staff will have a list of contacts as participant issues or concerns arise that need medical or psychiatric attention, or when other types of referral or assistance are needed. Individuals who report suicidal intent or other severe psychiatric symptoms or medical problems will be referred for treatment and followed throughout the study period. Continued participation with the study will be voluntary and in cooperation with the health care professional treating the subject's psychiatric or medical condition.

The study staff will be trained by [name], licensed clinical psychologist, and Dr. [REDACTED] [REDACTED], Mayo Clinic Board Certified Psychiatrist, to observe and monitor depression and psychiatric symptoms. They will be available to consult with the study staff as needed.

In the event a participant withdraws from the study or the LI decides to discontinue a participant due to an SAE, the participant will be monitored by the LI via ongoing status assessment until:

- (1) Resolution is reached (i.e., the problem requiring treatment has resolved or stabilized with no further changes expected)
- (2) The SAE is determined to be clearly unrelated to the study intervention
- (3) The SAE results in death.

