10.3.8 Follow-Up

Assessments will be conducted at the end of the intervention with a six-week visit window for completion (King et al., 2020). The participants will complete a UDS and a Follow-up Survey (by phone or in-person at the UDS visit). Study staff will attempt to contact the participant up to three times to complete the assessments and additionally reach out to the participant's secondary contact as needed. If the participant cannot be contacted within the six-week visit window, they will be considered lost to follow-up. Participants will receive a \$ [REDACTED] cash card for completing the Follow-Up Survey. They will receive an additional \$ [REDACTED] [REDACTED] cash card for completing the in-person UDS as a thank you for their time and for any travel costs incurred.

Follow-up Survey measures will evaluate treatment satisfaction and user experience using the Social Media Usability scale as well as four open-ended questions. It will also ask for the participant's thoughts on the potential for the group to be used as a way to encourage women to start their recovery journey and whether the participant would be interested in a peer moderator role for a future Facebook group. The TLFB will be used to assess opioid, opiate, and fentanyl use and MOUD use for each day since the previous TLFB assessment conducted at screening. We will again collect information on other OUD treatments the participant completed within the 30 days during the intervention. Using the TLFB, we will again assess for other substance use including stimulant use such as methamphetamines, cocaine/crack and marijuana use. The UDS

will be conducted in-person and staff will follow the same procedures as described above for the screening visit.

The Follow-Up Survey will include the same items from WHOQOL SRPB as the Baseline Survey to assess any changes in how their spirituality affects their Quality of Life and the K6 scale to assess changes in psychiatric symptoms during their participation in the Facebook group. It will also ask how important the participant feels it would be for Facebook groups like the pilot group to address spirituality from 0=not at all important to 10=very important. The study staff will assess adverse events (AEs) and serious adverse events (SAEs) including self-reported trips to the emergency department (ED), hospitalizations, and overdoses since enrollment.

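### Section 12 lets the study end a woman's follow-up for any reason, and no end assessment is requested when the removal does not follow an adverse event

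*Combined protocol and SAP*

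**What the plan says.** Under Section 12 each woman is "followed for the duration of the study CTN-0123 unless they withdraw consent, die, or the investigator or sponsor decides to discontinue their enrollment", and it allows that decision for any reason. Its list of reasons is open-ended. Four of the six concern the individual woman: "The participant becoming a threat to self or others", "The participant not following instructions", "The participant relapses on opioids while pregnant", and harm from staying in the study. The other two, lack of funding and cancellation, concern the study as a whole. The only exit step in Section 12 is advice on safety tests, given where it discusses voluntary withdrawal.

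Other sections do seek data at or after exit:

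- Appendix A (Participant Withdrawal) asks a woman who withdraws voluntarily to complete an end-of-intervention visit.
- Appendix B (2.0 E, Participant Protection) stops the intervention after an adverse event (AE) that makes participation unsafe, and requests the same visit.
- Section 10.3.7 completes the remaining procedures for women who leave the intervention but stay in the study. It adds that "Individuals who report suicidal intent or other severe psychiatric symptoms or medical problems will be referred for treatment and followed throughout the study period". Where "the LI decides to discontinue a participant due to an SAE, the participant will be monitored by the LI via ongoing status assessment", the monitoring concerns the event and not the study outcomes.

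Pregnancy is no bar to entry: "Pregnant women, lactating women, or women who plan to become pregnant will not be excluded" (8.4).

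**The concern.** The analysis includes all enrolled women and replaces none (17.3.3), and the protocol elsewhere separates leaving the Facebook group from leaving the study. Section 12 lets the study itself end both at once, for reasons that can be tied to adherence or to the exploratory outcome, and says nothing about collecting the planned end data.

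A woman removed in that way before Time 2 would have no follow-up survey (usability score and open-ended feedback), repeat K6, TLFB, urine drug screen (UDS) or structured questions on emergency visits, hospitalizations and overdoses. Monitoring of a known serious event and spontaneous reports would remain. She would count as not retained, and retention is a secondary outcome. The seven-consecutive-day relapse summary and the MOUD-days summary rest on daily reports from the end TLFB, so neither would be available for her. Each woman is one tenth of the Phase 3 sample.

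**Working it through.** **1. Which exits carry an end assessment**

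| Route out | Source | What is sought at the end |
|---|---|---|
| Stops using the group, stays in the study | 12 (last sentence), 10.3.7 | All remaining procedures |
| Voluntary withdrawal | Appendix A | End-of-intervention visit |
| AE that makes participation unsafe | Appendix B | Intervention stopped; end-of-intervention visit |
| Leaves or is discontinued in connection with a serious AE | 10.3.7 | Status monitoring of the event |
| Removed by investigator or sponsor, no AE | 12 | Nothing stated |

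The last row is the gap.

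**2. Which individual reasons fall in that row**

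- Not following instructions is not in itself an AE, so it falls there clearly.
- Threat to self and harm from staying may often follow an AE, and Appendix B would then request the visit.
- Relapse while pregnant is undecided. Section 18.19.1 does not name relapse among reportable AEs, but Appendix B is triggered by any AE that makes participation unsafe, and Appendix A defines AEs broadly.

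**3. Size**

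There is no figure in the plan to reproduce: N = 10 (8.2, 17.2.2.2) rests on guidance for early-stage development, and the analyses are descriptive. The documents give no removal rate and none is assumed here.

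Retention is the share of enrolled women who complete both the survey and a UDS (17.3.2.2). With k removals lacking Time 2, its maximum is (10 − k)/10: 9/10 = 90% for k = 1 and 8/10 = 80% for k = 2. If Time 2 is completed, it can be 10/10.

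For relapse, take one removed woman without Time 2 data and let r of the other nine relapse. Section 17.3.3 plans two codings: missing=relapsed, and missing=missing. The second is read here as dropping her from the denominator.

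*Removed woman abstinent.* Truth = r/10. Missing=relapsed = (r + 1)/10, error +1/10. Missing=missing = r/9, error r/9 − r/10 = r/90.

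| r | Truth | Missing=relapsed | Error (points) | Missing=missing | Error (points) |
|---|---|---|---|---|---|
| 0 | 0% | 10% | +10 | 0% | 0 |
| 1 | 10% | 20% | +10 | 11.1% | +1.1 |
| 2 | 20% | 30% | +10 | 22.2% | +2.2 |

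*Removed woman relapsed, and her disclosure is not counted as self-report.* Truth = (r + 1)/10. Missing=relapsed = (r + 1)/10, error 0. Missing=missing = r/9, error r/9 − (r + 1)/10 = −(9 − r)/90.

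| r | Truth | Missing=relapsed | Error (points) | Missing=missing | Error (points) |
|---|---|---|---|---|---|
| 0 | 10% | 10% | 0 | 0% | −10.0 |
| 1 | 20% | 20% | 0 | 11.1% | −8.9 |
| 2 | 30% | 30% | 0 | 22.2% | −7.8 |

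If her disclosure does count as self-report, she is a relapse under both codings and the negative errors vanish. If the second coding instead means that missing is counted as not relapsed, it gives r/10: correct for the abstinent woman and 10 points too low for the undisclosed relapser. With Time 2 done, and taking its results as accurate, both codings return the truth.

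For scale, the exact 95% interval for 1/10 runs from 0.3% to 44.5%.

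**The case against.** The strongest reply is that other text already narrows the gap, and much of that reply stands.

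- A reader might infer that a woman who relapses while pregnant is certain to leave without an end assessment, so that follow-up stops because of the outcome. The documents do not support this. Under the broad AE definition in Appendix A the relapse may well qualify, and Appendix B would then request the visit. Nothing settles the point either way.
- A reader might also infer that missing=missing always loses a known relapse. Section 17.3.2.3 counts a positive UDS or self-report and does not confine self-report to the TLFB, although 7.3 names the TLFB as the instrument. The lead coding counts her as relapsed in any case.
- The commonest non-adherence, not engaging with the group, need not end follow-up (last sentence of Section 12, with 10.3.7). Breaches of group rules can be met by removing posts (10.3.5).
- Discretion is not wholly unchecked: 18.19 and Appendix B provide for a clinician's advice on withdrawal decisions, although the appointment is optional.
- Section 12 is permissive, so it overlaps with Appendix B and 10.3.7 and does not contradict them.
- No single coding is right for every missing outcome. Reporting two is a reasonable sensitivity analysis, and counting a removed woman as not retained follows the stated definition.

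A reader might further infer that the study would misreport a removed woman as lost. Section 10.3.8 says "If the participant cannot be contacted within the six-week visit window, they will be considered lost to follow-up", while 17.3.3 extends that label to anyone who does not complete the follow-up tasks. But the Study Completion Form (10.3.12) records each woman's status and its fields are not shown, so the reason may already be captured. That is at most a missing detail.

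None of this supplies an end assessment after removal without an AE.

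**Conclusion.** The point holds, and it is minor. Section 12 permits a study-initiated end to follow-up for any reason, and no section requests Time 2 data when that removal does not follow an AE. Not following instructions is the clear case; relapse while pregnant is an open one.

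Per removal, retention is capped 10 points lower, and an abstinent woman raises the missing=relapsed figure by 10 points. For a known relapser, missing=missing is too low by 7.8 to 10.0 points, on three assumptions: she has no Time 2 data, her disclosure is not counted as self-report, and up to two of the other nine relapse.

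The weight is small because relapse is exploratory, the summaries are descriptive, and no decision rule depends on them. UDS and TLFB are done only at screening and Time 2, so an earlier removal for relapse would need a spontaneous or online disclosure. Few or no removals are likely. The case for acting is that end data and safety information can be kept at almost no cost.

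**What to change.** Add two sentences to Section 12. The first: when the study removes an individual woman, only her access to the group ends, and the planned Time 2 survey (with K6, TLFB and AE questions, by phone where possible) and UDS are still sought. The second gives the exceptions: she withdraws consent, Section 18.12 requires suspension, a clinician judges contact harmful, or the whole study is cancelled. Cross-refer to Appendix B for removals that follow an AE, and to 10.3.7. Keep N = 10 and both planned codings.

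This needs no new visit, because Time 2 is already planned. The cost is a little effort to reach women who have left the group. If the Study Completion Form has no entry for the reason for removal, adding one would help but is not essential.

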13. STUDY HALTING RULES

Specific stopping rules have been developed to protect the safety of our study subjects enrolled in Phases 1 or 3. In the case of any SAE, the study will be stopped and no further enrollment will take place until an investigation of the event has taken place by the LI ([name]), or a Co-LI.

If the SAE involves death or a life-threatening event, the LI, [name], will be notified immediately by the study staff. [name] will telephone, fax, and/or e-mail the Mayo Clinic IRB with follow up notifications to the NIDA Program Official within 24 hours of when she learns of the event. This telephone contact will be followed up with a standardized report form submitted to both the IRB and NIDA within 2 working days of the study staff learning of the SAE. If the SAE involves something other than death or a life-threatening event, [name] will submit a standardized, detailed report of the event to the IRB and NIDA within 2 working days of when the SAE was reported. Reports of serious adverse events received by the IRB will be reviewed by an institutional SAE Board, (the members of these boards are not involved in this study) to decide of the seriousness of the event and to determine what actions, if any, will be required. If the SAE Board determines that suspension or termination of the study is required, this information will also be reported to NIDA within 24 hours.

Outcome of SAEs will be reported bi-annually to NIDA or as otherwise specified by the NIDA Program Official. A summary of the SAEs that occurred during the previous year will be included in the annual progress report to NIDA and to IRB. All protocol changes and/or protocol amendments will be reported to NIDA, then the IRB. Additionally, a summary of all AEs will be reported in an annual progress report to the IRB. A determination of the association of the adverse event with the study intervention will be made and appropriate modifications to the protocol will be made if an association is suspected. If protocol modifications to ensure the safety of future study subjects cannot be made, the study will be terminated.

14. PARTICIPANT REIMBURSEMENT/REMUNERATION

Participants will be compensated for the participation in this study. Compensation will be in accordance with the Mayo Clinic IRB policies and procedures, and subject to IRB approval.

Participants in all phases of the study will receive compensation via a mailed Mayo Clinic Credit Union cash card. The study staff will assign a cash card ID to the participant, which will be noted in REDCap for reference when documenting payments in Mayo Clinic's Research Participant Payment Application (RPPA).

With Research Finance, the study team will document all participant payments in RPPA and the study team will ask the participant for their SSN. If they decline, the study staff will mark that the participant does not have an SSN.

15. DISSEMINATION

With input from the CAC, the research team will create a study newsletter to share the findings in aggregate from both phases of the research. This will be mailed to participants in Phases 1 and 3 who provided their permission to be re-contacted for this purpose.

DRAFT

16. TRAINING REQUIREMENTS

16.1 Overall

A comprehensive Training Plan will be developed to incorporate general training, study-specific training, mechanisms for competency assessment as well as a detailed description of training, supervision, and fidelity monitoring procedures. The Investigative Team is responsible for the development of a comprehensive Training Plan, instructional material, and delivery of the training, with the team comprised of the Lead Node and other participating nodes and subject matter experts, as applicable.

The CTN-0123 study staff will be trained as specified in the study Training Plan. Training will include Human Subjects Protection (HSP) and Good Clinical Practice (GCP) as well as protocol-specific training on assessments, the study intervention, safety and safety event reporting, study visits and procedures, data management, quality assurance, etc. The Lead Node is primarily responsible for development and delivery of study-specific training related to the study intervention(s) and procedures. Other parties will contribute as needed based on the subject matter and material to be covered. The various sub-teams will collaborate to deliver quality instructional material designed to prepare research staff to fully perform study procedures based on the assigned research roles and responsibilities.

In addition to general and study-specific training, the Training Plan will include a description of the delivery methods to be used for each training module (e.g., via self-study, online, webcast, or teleconference). Study staff is required to complete institutionally required training per their research site, Institutional Review Board, and authorities with regulatory oversight. Tracking of training completion for individual staff as prescribed for assigned study role(s) will be documented and endorsed by the site LI and the Lead Node. As changes occur in the prescribed training, the Training Plan and training documentation tracking forms will be amended to reflect these adjustments.

16.2 Protection of Human Subjects

Key personnel have completed the required education on the protection of human research participants at their respective institutions. The Mayo Clinic has established a formal program entitled the “Mayo Investigator Training Program” (MITP). The MITP is a web-based educational course designed to provide all personnel involved in human subject research with training about human subject protection. All Mayo personnel engaged in human subject research are required to complete the course. MITP primary objectives are to provide historical context for human subject protection regulations and explore the evolving issues for human subjects research.

17.0 STATISTICAL DESIGN AND ANALYSES

17.1 General Design

17.1.1 Study Hypothesis

We hypothesize that by using a CBPR approach, input from recovering AIAN participants and our CAC, content refinement, a comprehensive moderator exchange, and a beta test of the intervention with recovering AIAN participants will result in a culturally relevant Facebook intervention prototype to support recovery from illicit opioid use.

17.1.2 Primary and Secondary Outcomes (Endpoints)

Primary Outcome: A culturally relevant Facebook intervention prototype to support recovery from opioid use.

Secondary Outcomes: Recruitment feasibility, study retention, level of intervention engagement, and intervention satisfaction.

Exploratory Outcome Measures: Abstinence from opioid use and MOUD retention at the end of the intervention.

17.2 Rationale for Sample Size and Statistical Power

17.2.1 Projected Number of Sites

This study will have one site.

17.2.2 Projected Number of Participants

17.2.2.1 Phase 1

Using a stratified purposeful sample (Patton, 2015), we estimate up to 18 interviews with AIAN women participants and 12 interviews with interested parties, based on recommended guidelines for the number of individual qualitative interviews needed to reach data saturation (Namey et al., 2016). Data saturation is the point at which no new information is being learned (Krueger, 2014; Saunders et al., 2018). Recruitment of these additional participants should be feasible within our study timeline. We will consult with members of our Community Advisory Committee as needed as several represent AIAN healthcare and community organizations, thus we do not foresee a need to increase the number of stakeholder interviews.

17.2.2.2 Phase 3

A sample of $N=10$ AIAN women participants is consistent with recommendations for Stage 1a behavioral addictions treatment development (Rounsaville et al., 2001) and beta-testing of novel digital and mHealth interventions (Baker et al., 2014; Nielsen, 2012). Moreover, 10 was the minimum number of participants for optimal Facebook intervention engagement in prior studies (Ramo et al., 2015).

